Our modelling work shows that HCV treatment is a critical component to HCV prevention among people who inject drugs and is likely to be cost-effective compared to delaying treatment or treating non-PWID with mild or moderate disease (7-11). For example, we show in a number of settings with chronic HCV in PWID below 60% that treating 10-20 per 1000 drug users per year can reduce HCV prevalence by 50-90% over 10-15 years; that for every one PWID treated in the 20% chronic HCV setting 2 new HCV infections are averted. The scale of the benefit is inversely and exponentially related to prevalence of HCV in the population, the lower the prevalence the sooner and bigger the impact.

Current conventional treatment pathways focus on populations drawn from those known to drug problem services and former drug users. Treating people who are the most stable and with a low risk of relapse back into chaotic injecting will reduce future morbidity in the individual patients but may not achieve additional benefit in terms of averting future infections. Our recent work within Tayside has shown that we are able to test less stable, actively injecting drug users for Hepatitis C and then successfully treat them using both the conventional care pathway and non-conventional care pathways, such as needle exchange clinics (e.g. Eradicate study, completed February 2017; Advance study, started in January 2018, ongoing), community pharmacies (SuperDOTC study, December 2016 – January 2019. REACH HCV study, started February 2020, ongoing) and prisons (12). If the models are correct, this intensive treatment programme will effectively eradicate Hepatitis C from Tayside over the next few years. However, the models are not yet empirically tested and they make some assumptions that if violated may lead to over or under-estimation of the intervention effect. For example, the models assume that (a) heterogeneity in injecting risk and uptake of HCV testing and treatment will even out as PWID move and transition between high and low risk periods; and (b) that HCV transmission risk for susceptible PWID is similar for those that have achieved SVR or are untreated.

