2 BACKGROUND & RATIONALE

We have embarked on a series of studies that will dramatically increase the number of PWID with HCV infection who are being treated. This allows us to test empirically modelling data predicting treatment as prevention works for HCV infection. We are aiming to treat enough people actively injecting drugs who are infected with Hepatitis C in Tayside to reduce the prevalence in this population from approximately 29% to less than 10%. This will reduce the incidence of new infections from over 5% per annum to less than 1% per annum which we can detect with population surveillance techniques.

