6 DATA COLLECTION & MANAGEMENT

6.1 DATA COLLECTION

Details of all patients who are undergoing or have completed HCV treatment in Tayside are entered into a clinical database as per standard care by specialist HCV nurses and this practice will continue as we intensify treatment rates through our clinical trials and NHS treatment pathways. Data in this database will form the source for treatment initiation and outcomes. Twice a year the number of patients treated and cured since last data extraction will be extracted with no patient identifiable information but with data on viral genotype, stage of liver disease, pathway of treatment delivery and current drug use status.

Data on infection rates from routine HCV testing within NHS Tayside is also collected in the virology service in Tayside for government reporting. On a six monthly basis we will extract data on known HCV negative patients who have been retested in that time period. The data extraction will consist of the date when they were last known to be negative, the date of re-test and the result of the test. No patient identifiable data will be used.

Population level data will be collected 6 monthly around the anniversary of the study commencement or to coincide with the NESI data collection cycles.

The source data will be accessed by the clinical care team and clinical data which is not patient identifiable entered into the study data management system which will be built within Excel and held on a University server that is GCP compliant; regularly backed-up, has access controls and updates to operating system and security software. Caldicott approvals will be obtained as required.

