6.2 DATA MANAGEMENT SYSTEM

Data management will be conducted in compliance with TASC SOPs on Data Management, including TASC SOP33 Data Management to GCP standards and TASC SOP53 Data Management Systems in Clinical Research.

The data management system (DMS) will be Excel. The data will be used to calculate the treatment rate and cure rate for the time period and the rate of new infection. The core data will then be destroyed. The anonymized dataset may be shared with colleagues in other UK Universities. The database is managed in line with all applicable principles of medical confidentiality and UK law on data protection, namely, the Data Protection Act 1998, which brought UK law into line with the EU Data Protection Directive. The Data Controller will be the University of Dundee and the Data Custodian will be the CI.

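### The only specified incidence source is retested known negatives with no injecting status or test setting, so the rate cannot be limited to PWID or adjusted for changes in who is retested

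*Combined protocol and SAP*

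**What the plan says.** Section 6.1 (Data collection) describes two routine extracts.

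- **Virology extract, for infection.** Every six months the study will "extract data on known HCV negative patients who have been retested in that time period". Its content is "the date when they were last known to be negative, the date of re-test and the result of the test". The section adds: "No patient identifiable data will be used".
- **Treatment extract, for numbers treated and cured.** This one carries, among other items, "pathway of treatment delivery and current drug use status".

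Section 6.1 also mentions six-monthly population-level data, timed to the study anniversary or to NESI cycles, without listing their content.

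Section 6.2 states the use: "The data will be used to calculate the treatment rate and cure rate for the time period and the rate of new infection". It continues: "The core data will then be destroyed".

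Section 4.11 includes everyone eligible for HCV testing and treatment in NHS Tayside. Its list goes well beyond injecting: unexplained raised liver enzyme, HIV, past blood products, occupational exposure, tattoos, household contact, and anyone who thinks they are at risk.

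Section 2 sets the expected effect in PWID: to "reduce the incidence of new infections from over 5% per annum to less than 1% per annum".

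**The concern.** The study has no control region of its own, so its evidence on incidence is a trend over time. A rate from retested people tracks transmission only if the risk profile of those people stays stable or can be adjusted for. Neither is secured here: the listed fields do not show who injects, where the test was done, or how many known negatives were not retested.

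A change in that profile is plausible. Section 1 reports that "we are able to test less stable, actively injecting drug users for Hepatitis C", and describes care through needle exchanges, pharmacies and prisons. If such pathways bring more active injectors into retesting, the crude rate is pushed up and a real fall could be hidden. A shift towards lower-risk people would do the opposite.

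Two features make this hard to repair later. The extract has no identifiers, so it cannot be linked to drug-use status in the treatment extract. The core data are also destroyed; an anonymised dataset may be shared under 6.2, but it cannot contain more than was extracted. Under section 8.2 these incidence measures are then to be compared with other UK regions, so any distortion carries forward.

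Separately, a person already infected at a first test has no earlier negative and cannot enter this extract.

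**Working it through.** **1. The plan's own figure.** There is none to reproduce. Section 7.1 gives 2,800 as a population estimate, with no number retested, retest rate, precision or power. All risk rates and shares below are assumptions.

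**2. What the rate can be conditioned on.** For each retested person the extract gives time at risk (the interval between two dates) and the outcome. It therefore yields the number retested, test intervals and a crude rate. Restriction to PWID needs an injecting marker, and adjustment for retest selection needs characteristics of the retested and of the known negatives they came from. Neither is listed.

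**3. Effect of a mix shift with transmission unchanged.** Let s be the active-injector share of retests, and a and b the yearly rates in active injectors and others. The observed rate is r = s·a + (1 − s)·b. With a = 5% and b = 0.5%:

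- s = 30%: 0.3 × 5 + 0.7 × 0.5 = 1.85%
- s = 60%: 0.6 × 5 + 0.4 × 0.5 = 3.20%

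Upwards, 3.20/1.85 = 1.73, a false 73% rise. Downwards, 1.85/3.20 = 0.58, a false 42% fall.

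The relative change depends only on the shares and k = a/b. The ratio is [1 + 0.6(k − 1)] / [1 + 0.3(k − 1)]:

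- k = 10: 6.4/3.7 = 1.73
- k = 20 (for example 10% and 0.5%): 12.4/6.7 = 1.85, a false 85% rise or, reversed, a 46% fall
- k = 1: no distortion

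**4. A real fall hidden.** Take a = 10% and b = 1%. A share of 44.4% gives 5.0%, near the baseline in section 2. Now halve both true rates, to 5% and 0.5%:

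- share unchanged: 2.5%, and the halving is seen in full
- share 60%: 0.6 × 5 + 0.4 × 0.5 = 3.2%
- share 80%: 0.8 × 5 + 0.2 × 0.5 = 4.1%
- share 100%: 5.0%, and the halving disappears

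**5. Why numbers do not cure it.** At 29% prevalence, 2,800 × 0.71 = 1,988 people are susceptible. Comparing 5% with 1% (two proportions, two-sided 5% level, 80% power) needs 285 retested per period, and 285/1,988 is about 14%. So a modest retest fraction could give adequate precision while saying little about who was left out. More retests also make a spurious change likelier to reach significance. With fixed rates of 10% and 1%, a share falling from 44.4% to 20% moves 5.0% to 2.8%, which would be declared a fall with probability 0.36 at 400 per period, 0.62 at 800 and 0.72 at 1,000.

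**6. Infections before a first test.** Let h be the rate in people eligible for the extract, c·h the rate before a first test, and p the share of susceptible person-time before a first test. The rate in everyone is h·[1 + p(c − 1)]; the extract estimates h. If c = 1 the two agree, because the missed infections leave together with their person-time. Bias in the level requires c ≠ 1, and bias in the relative trend requires p or c to change over time. The documents give neither.

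**The case against.** The strongest reply is that the retest series does not stand alone. Section 4.11 names NESI as a source, 6.1 plans population-level data, section 2 has a prevalence target (about 29% to below 10%) as well as an incidence one, and 7.2 measures the primary outcome by evidence synthesis and transmission models that are meant to account for bias. This stands as far as it goes. A reader might infer that the retest trend is the study's only evidence of effect; the documents do not support that. It is the only incidence source they specify. They state no incidence role for NESI, and a synthesis can correct for selection only if it has information about it. Numbers retested and test intervals give some, but not on risk mix.

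A reader might also infer that a false fall is to be expected. The text points the other way: outreach to active injectors would raise the crude rate. Section 1 also does not say that testing will move between settings during the study, and some of its pathway studies are already complete. Nor does the 5%/0.5% example reproduce the planned effect: to go from 5% to 1% on mix alone, the active share would have to drop from 100% to (1 − 0.5)/(5 − 0.5) = 11%.

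Finally, it is tempting to read infections before a first test as a large undercount in the rate. A steady-state calculation from 29% prevalence, 5% incidence and 75% chronicity gives turnover of 0.75 × 0.05 × 0.71/0.29 = 9.2% a year, or 257 entrants. With first tests at 1 to 2 years, 257 × (1 − exp(−0.05t)) = 12.5 to 24.5 of about 99 yearly infections (0.05 × 1,988), or 13–25%, fall outside the extract. That is a share of infections, not a bias in the rate (step 6). It also ignores treatment. With 10–20 per 1,000 treated a year and 90% cured, turnover is (0.026625 − 0.009)/0.29 = 6.1% to (0.026625 − 0.018)/0.29 = 3.0%, and the share falls to about 4–16%.

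**Conclusion.** The point holds as a limit on what the extract can show. As written, the rate of new infection mixes injecting and non-injecting people and cannot be adjusted for a change in who is retested. Under assumed rate ratios of 10 to 20, a move between 30% and 60% active injectors shifts the observed rate by 73–85% upwards or 42–46% downwards with no change in transmission. These figures show sensitivity and are not estimates, since the documents give neither the mix nor the rates. They show that distortion can occur, not that it will. The direction that section 1 makes more plausible is a hidden benefit. The omission of infections before a first test is a secondary matter, and biases the rate only if risk before a first test differs from risk in retested people. The change is worth making while the fields can still be requested.

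**What to change.** Amend 6.1 so that each six-monthly virology extract adds the following, where the source holds them and before core data are destroyed:

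1. a PWID marker and test setting for each retest and for the last negative test;
2. the number of known negatives at the start of the period, by those same last-negative-test characteristics;
3. first-ever tests in the period, with result.

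In 7.2, make the PWID-restricted rate the main incidence series and report retest coverage each period. Beside the crude rate, show one standardised to the baseline mix or weighted for retest selection. The weights must use last-negative-test characteristics, because setting in the current period is undefined for people not retested. Enter first-test positives in the evidence synthesis as a separate data stream.

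The cost is a few fields and counts from a query already planned, plus one standardised or weighted analysis. That the virology records hold setting and PWID status is an assumption, and both may be incomplete. Known-negative counts may include people who have died or moved, standardising by setting leaves the risk mix within a setting unadjusted, and the wider extract may need further Caldicott approval. The crude rate should therefore still be reported.

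### The virology retest extract has no stated PWID restriction and no injecting-status or test-setting field, so a new-infection rate from it may mix PWID with non-PWID, and the study dataset could not show this

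*Combined protocol and SAP*

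**What the plan says.** Section 4.9 and the synopsis define the study population as PWID in Tayside, about 2,800 people. Section 2 aims to bring incidence in that population from over 5% to under 1% per year.

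Section 6.1 describes the retest source thus: "Data on infection rates from routine HCV testing within NHS Tayside is also collected in the virology service in Tayside for government reporting". Every six months, "we will extract data on known HCV negative patients who have been retested in that time period". Each record holds "the date when they were last known to be negative, the date of re-test and the result of the test", and "No patient identifiable data will be used". The treatment extract in the same section is richer: its fields include "pathway of treatment delivery and current drug use status". Section 6.1 also provides for other input: "Population level data will be collected 6 monthly around the anniversary of the study commencement", or timed to the NESI cycles.

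Section 6.2 then says: "The data will be used to calculate the treatment rate and cure rate for the time period and the rate of new infection". The next sentence reads: "The core data will then be destroyed".

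Section 5.1 identifies participants through the inclusion criteria. The synopsis and section 4.11 set these as everyone eligible for HCV testing and treatment. Section 7.2 measures the primary outcome by evidence synthesis combined with infectious disease models, and says that uncertainty and bias across sources will be taken into account.

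**The concern.** The aim is about PWID, but the stream that looks set to supply incidence is not limited to PWID by anything written in the plan. Nor does it carry a field by which it could be limited later. If non-PWID are among those retested, and their infection rate is lower, the calculated rate sits below the PWID rate. If the mix of people retested changes over the study, the trend is distorted in one direction or the other.

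Both level and trend matter. The trend is the evidence that treatment works as prevention. The level feeds the cost-effectiveness models (section 3, Table 2) and the planned comparison with other UK regions (section 8.2), where even a stable mix need not cancel if it differs by region.

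A changing mix is plausible but not shown. Section 1 describes testing and treatment of active injectors through needle exchanges, pharmacies and prisons, with studies starting in December 2016, January 2018 and February 2020. The documents do not say that these changed who appears among routine retests.

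**Working it through.** **Reading the text**

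1. Records: known HCV-negative patients who were retested, from routine testing across NHS Tayside (6.1). No PWID filter is stated.
2. Fields: two dates and a result (6.1), worded as the full content of the extract. The same section lists drug use status and treatment pathway for the treatment extract only.
3. Upstream: section 4.11 lists eleven groups to be offered testing, of which one is defined by injecting. Section 5.1 relies on these criteria, so no restriction comes from there.
4. Use: section 6.2 does not name the source of the new-infection rate. That it is the retest extract is an inference, since this is the only described stream with the dates and results such a rate needs.
5. Recovery: the extract has no identifiers and no linkage is described, so status cannot be added within the study dataset. The virology source could in principle be extracted again, but the plan does not provide for it.

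**Size, by illustration**

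The plan gives no figure for the mix. Its own target, taken at the round values 5% and 1%, is a fall of (5 − 1)/5 = 80%. A partial fall from 5% to 3% (40%) is my choice, to show the effect on a smaller change.

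Mixed rate = (1 − s) × P + s × n, where s is the non-PWID share of retest person-time, P the PWID rate and n the non-PWID rate (% per year). Both s and n are assumptions. I take n = 0.05, with the range n = 0 to 0.2 in brackets.

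*Stable mix, P from 5 to 1*
- s = 0.1: 0.9 × 5 + 0.1 × 0.05 = 4.505, then 0.9 × 1 + 0.005 = 0.905. Fall 79.9% (79.6 to 80.0%).
- s = 0.2: 4.01, then 0.81. Fall 79.8% (79.2 to 80.0%).

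*Changing mix, P from 5 to 3 (true fall 40%)*

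| s at start → end | Mixed rate, % | Apparent change |
|---|---|---|
| 0.2 → 0.1 | 4.01 → 2.705 | −32.5% (−32.5 to −32.7) |
| 0.1 → 0.2 | 4.505 → 2.41 | −46.5% (−46.0 to −46.7) |
| 0.6 → 0.3 | 2.03 → 2.115 | +4.2% (+1.9 to +5.0) |
| 0.3 → 0.6 | 3.515 → 1.23 | −65.0% (−62.9 to −65.7) |

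*Changing mix, P constant at 5.* If s rises from 0.2 to 0.6, the mixed rate goes from 4.01 to 2.03, an apparent fall of 49.4% (47.5 to 50.0%) with no real change.

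*Break-even.* A fall from P0 to P1 is wholly hidden if the PWID share rises by the factor (P0 − n)/(P1 − n).
- 5 to 3: 4.95/2.95 = 1.68 (1.67 to 1.71), for example from 40% to 67%. This is impossible if the PWID share starts above 60%.
- 5 to 1: 4.95/0.95 = 5.2 (5.0 to 6.0). This is impossible if the PWID share starts above 20%.

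**The case against.** The best reply is that a PWID scope is intended. Section 7.1 puts everyone eligible at 2,800, the same figure that section 4.9 gives for PWID alone, and the synopsis says the PWID population will be monitored. The care team accesses the source data before entry (6.1) and could filter there. This makes the intention plausible. It does not state a filter, and it conflicts with the list in 4.11.

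The opposite reading is that a region-wide rate is wanted, since the primary outcome and section 8.2 speak of NHS Tayside. Mixing would then be no error in that measure, but this stream would not measure the PWID target in section 2.

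Third, the primary outcome rests on evidence synthesis, and NESI and population-level data are also collected. These may supply separate PWID evidence. But no stated input gives the PWID share of retests, which the synthesis would need in order to correct this stream. NESI's fields are not described, so this cannot be tested further.

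Fourth, the effect may be small, and this stands. Section 4.11 lists groups to be offered a test, not groups retested, and the only repeat testing the plan states is of PWID after treatment (Table 2). The 30% to 60% shares and the 5% to 3% fall above have no basis in the documents, and the full planned fall could hardly be hidden.

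Finally, section 6.2 allows an anonymised dataset to be shared, so some data may persist. That does not help if status was never extracted.

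**Conclusion.** The concern holds. Followed exactly as written, the plan yields a retest stream that cannot be restricted to PWID, and a study dataset that could not tell a negligible distortion from a large one.

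The consequence is limited. It affects one input to the synthesis and does not show that the primary result is uninterpretable. Size and direction are unknown. A stable mix lowers the level but nearly preserves the relative fall; a changing mix distorts the trend, and partial falls are more exposed than the planned 80%.

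This rests on the inference that the new-infection rate comes from the retest extract, on nobody applying an unstated filter, and, for the figures, on assumed shares and an assumed non-PWID rate of 0 to 0.2% per year. It should be fixed, since the remedy is cheap.

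**What to change.** If the extract is meant to cover PWID only, say so in 6.1 and state how PWID status is determined. Otherwise:

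1. **6.1:** before release, the care team adds to each retest record a non-identifying injecting-history flag (current, ever, none, unknown). Where history is not held, test setting (needle exchange, pharmacy, drug service, prison, other) can serve as a proxy.
2. **6.2:** before core data are destroyed, save an aggregate table of retests, person-time and new infections by six-month period and by PWID status or setting.
3. **7.2:** use the PWID stratum as the incidence input to the synthesis and report the PWID share of retests in each period. Add a sensitivity analysis that assigns unknown-status records all to PWID, then all to non-PWID.

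The cost is protocol wording, one field and one saved table. The documents do not say that virology holds injecting history or test setting, so linkage by the care team and an updated Caldicott approval may be needed. Some records will have unknown status, small cells may need suppression, and intervals for the PWID stratum will be wider.

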SVR12	Sustained viral response at least 12 weeks after end of treatment
SMG	Management Group
TSC	Trial Steering Committee

SUMMARY/SYNOPSIS

Study Title	Evaluating Treatment as Prevention among People Who Inject Drugs in Dundee for HCV (E-raPiD-HCV)	
Study Design	The aim of this study is to conduct an evaluation of hepatitis C treatments in NHS Tayside in order to empirically test the “treatment as prevention” models. This will be done by analysing the records of patients who have been tested and treated for hepatitis C using NHS Tayside databases. There will be no interventions carried out as part of this study.	
Study Population	This study will monitor the target PWID population (we estimate approximately 2,800 individuals) as we intensify the number of treatments provided to this population and achieve levels of treatment that will test the “treatment as prevention” concept.	
Sample Size	Approximately 2,800 individuals	
Planned study Period	6 years	
Primary	Objectives To demonstrate treatment as prevention reduces HCV.	Outcome Measures HCV testing in NHS Tayside
Secondary	Objectives To develop the analytic framework that can be used to assess the impact of treatment as prevention, incorporating evidence from multiple sources and taking into account uncertainty and bias	Outcome Measures Numbers of patients engaged in treatment and SVR ₁₂ during the treatment phase
	Objectives To develop dynamic cost-effectiveness models of HCV treatment among PWID	Outcome Measures Costs of treatment pathways and infection rates
	Objectives Re-infection with HCV following treatment	Outcome Measures Annual routine offer of HCV testing
Inclusion Criteria	All individuals in NHS Tayside eligible for HCV testing and treatment according to Scottish Intercollegiate Guidelines Network guidelines.	
Exclusion Criteria	None	

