3 STUDY OBJECTIVES & OUTCOMES

Table 1: Primary Objectives and Outcome Measures

Primary Objective:	Outcome Measure:	Timepoint of outcome measured
To demonstrate treatment as prevention reduces HCV.	HCV testing in NHS Tayside	Annually

Table 2: Secondary Objectives and Outcome Measures

Secondary Objective:	Outcome Measure:	Timepoint of outcome measured
To develop the analytic framework that can be used to assess the impact of treatment as prevention, incorporating evidence from multiple sources and taking into account uncertainty and bias	Numbers of patients engaged in treatment and SVR ₁₂ during the treatment phase	Years 1-3
To develop dynamic cost-effectiveness models of HCV treatment among PWID	Costs of treatment pathways and infection rates	Year 5
Re-infection with HCV following treatment	Annual routine offer of HCV testing	Following treatment and subsequently annually for each PWID

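### Re-infection after treatment is a secondary objective, but the extracts and rates described in sections 6.1 and 6.2 cannot produce a re-infection rate

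*Combined protocol and SAP*

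**What the plan says.** The Synopsis and Table 2 of section 3 list "Re-infection with HCV following treatment" as a secondary objective. The outcome measure beside it is "Annual routine offer of HCV testing". Table 2 times it after treatment and then yearly for each person who injects drugs.

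Section 6.1 describes three data streams:

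- **Treatment extract.** Twice a year "the number of patients treated and cured since last data extraction will be extracted with no patient identifiable information", with genotype, liver disease stage, treatment pathway and current drug use status.
- **Retest extract.** From the virology service, every six months, "we will extract data on known HCV negative patients who have been retested in that time period". Its content is the "date when they were last known to be negative, the date of re-test and the result of the test".
- **Population data.** "Population level data will be collected 6 monthly around the anniversary of the study commencement or to coincide with the NESI data collection cycles".

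Section 6.2 then says: "The data will be used to calculate the treatment rate and cure rate for the time period and the rate of new infection". The next sentence is "The core data will then be destroyed". Section 7.2 describes evidence synthesis, infectious disease models and an economic evaluation, and does not mention re-infection.

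**The concern.** An offer of testing is an activity. A re-infection outcome needs positive results in people already cured, over the time they were at risk. To count these, each retest must be tied to whether the person had been treated and had reached SVR12. The described retest record carries no such item, and the treatment extract is a separate count.

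Two things are at stake. First, a stated secondary objective has no data specified that could answer it. Second, the content of the rate of new infection is left open, because the plan does not say whether cured people are among the known negatives. Section 8.2 says the Tayside incidence measures will be used in a larger multi-region study, so its users need to know what the rate contains.

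**Working it through.** **Step 1. What a re-infection rate needs, against what is described.**

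| Needed | Described |
|---|---|
| Positive retests in people cured by treatment | Retest result is present; prior treatment or SVR status is not (6.1) |
| Person-time at risk after cure | Two dates give an interval, but not whether it follows cure (6.1) |
| Link between treatment and virology records | None described (6.1) |
| Test type behind negative and positive | Not stated (6.1) |
| Injecting status, since Table 2 refers to PWID | In the treatment extract, not in the retest extract (6.1) |
| A re-infection rate among the outputs | Three rates named, none for re-infection (6.2); no mention in 7.2 |

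**Step 2. The two readings of known HCV negative.** If it includes people negative after SVR12, their re-infections enter the same rate as first infections. If it means never infected, re-infections fall outside the extract. Neither reading gives a separate re-infection rate.

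**Step 3. Under the first reading, the three fields cannot separate the parts.** Let w be the share of retest person-time that follows cure, f the first-infection rate and r the re-infection rate. Treating all person-time as one or the other:

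pooled rate = w·r + (1 − w)·f

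The documents give none of w, f or r for this extract. With w = 25% assumed, a pooled 2.0% a year fits all of these:

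- f = 1%, r = 5%: 0.25 × 5 + 0.75 × 1 = 2.0
- f = 2.67%, r = 0%: 0.75 × 2.67 = 2.0
- f = 0%, r = 8%: 0.25 × 8 = 2.0

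**Step 4. How far the pooled rate could sit from the first-infection rate.** With R = r/f, pooled/first = 1 + w(R − 1). All inputs are assumed.

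| w | R = 0.5 | R = 1 | R = 2 | R = 3 |
|---|---|---|---|---|
| 10% | 0.95 | 1.00 | 1.10 | 1.20 |
| 20% | 0.90 | 1.00 | 1.20 | 1.40 |
| 30% | 0.85 | 1.00 | 1.30 | 1.60 |
| 40% | 0.80 | 1.00 | 1.40 | 1.80 |

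**Step 5. How precise a comparison of the two rates could be.** This is illustrative and assumes an extract limited to PWID. Inputs: 2,800 people (4.9), and prevalence falling from 29% to 10% with incidence from 5% to 1% a year (section 2). Applying incidence to the uninfected:

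- start: 2,800 × 0.71 × 5% ≈ 99 infections a year
- target: 2,800 × 0.90 × 1% ≈ 25.2 a year

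With E infections in total and equal true risk, SE of the log rate ratio = 1/√(E·w·(1 − w)). At target incidence with everyone retested, the 95% intervals around a ratio of 1 are:

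| Period | E | w = 10% | w = 40% |
|---|---|---|---|
| 3 years | 3 × 25.2 = 75.6 | 0.47–2.12 | 0.63–1.58 |
| 6 years (Synopsis study period) | 6 × 25.2 = 151.2 | 0.59–1.70 | 0.72–1.38 |

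If half are retested over 3 years (E = 37.8), the intervals widen to 0.35–2.89 and 0.52–1.92. Higher early incidence would narrow them. Incidence below the 1% target would widen them.

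**The case against.** The strongest reply is that the route is under-specified rather than absent. Table 2 says whom to follow and when, the treatment database is named as the source for treatment outcomes, and the care team has access to the source records and could match them. That is fair, and it makes the remedy easy. But no matching step is written, and section 6.1 states what the retest extract will consist of. A team following the text would not produce the outcome.

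A second reply is that NESI data or the evidence synthesis in 7.2 will cover re-infection. The general framework there does draw on multiple sources, but no re-infection input is named, and the synthesis is tied explicitly to the primary outcome and objective.

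A third is that pooling is legitimate, since a re-infection is a new transmission. This stands. The request is to state what the rate contains and to report its parts as well.

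Three stronger readings are tempting, and the documents do not support them:

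- **That adding prior status alone would test assumption (b) in section 1.** That assumption, of similar risk after SVR and without treatment, concerns susceptible PWID. The eligible groups in 4.11 include many people who do not inject, and the retest extract has no injecting status. A ratio away from 1 could reflect case mix alone.
- **That the Tayside rate, or the regional comparison in 8.2, is biased.** The share of cured people among negatives is not given for any region, and the larger study's methods are not in these documents.
- **That destroying the core data loses the information for good.** The destruction concerns the study's data. The treatment and virology records are held for care and government reporting, so re-extraction may be possible.

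**Conclusion.** The point holds as a gap in what is described. From the extracts in 6.1 and the rates in 6.2, the re-infection objective cannot be answered: re-infections are either merged with first infections or excluded, and the plan does not say which. Confidence in this textual finding is high, subject to one limit: the front matter was not available, so a definition there cannot be excluded.

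The numerical consequence is unknown in size and direction. The factors of 0.80 to 1.80 follow from assumed shares and risk ratios and are not evidence of bias; at equal risk there is no distortion. The precision figures likewise rest on an assumed PWID-only extract, constant target incidence and equal retesting in both groups. They suggest that any comparison of re-infection with first infection would be imprecise. It would also be open to differences in who is retested.

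The direct effect is on a secondary objective. It should be fixed, but it does not by itself undermine the primary one.

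**What to change.** **Section 6.1.** Define HCV negative and a positive re-test by test type. Have the care team add to each retest record, before de-identification:

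- prior status: never infected, spontaneously cleared, treated with documented SVR12, treated without documented SVR12, or unknown;
- test type at both dates;
- PWID or injecting status.

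**Table 2.** Replace the offer of testing with RNA- or antigen-positive results after documented SVR12 per person-year at risk.

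**Sections 6.2 and 7.2.** Report first-infection, post-SVR re-infection and combined rates with confidence intervals, restricted to or stratified by PWID, before the core data are destroyed. Keep any comparison bearing on assumption (b) within PWID. Tell the larger study in 8.2 what the Tayside rate contains.

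**Cost.** A few non-identifying fields, record matching by staff who already access the source data, a Caldicott check, and a protocol amendment with Sponsor, REC and NHS R&D approval before use (12.1). The rule against patient-identifiable data is kept.
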